**3. PROTOCOL SYNOPSIS**

Name of Sponsor UCLouvain (ARC, Actions de Recherche Concertée – Di-Prescribe)
Title of Study Development and validation of a health behavior theory-based questionnaire to examine the willingness of older adults and informal caregivers to deprescribe
Service(s) in which the experimentation is taking place Primary care setting, nursing homes in Brussels and Wallonia
Publication (reference)
Studied period : September 2023 to october 2024
Objectives: - Primary: to develop and validate a health behavior theory-based questionnaire to examine the older adults’ and informal caregivers’ determinants of deprescribing behavior - Secondary: assess the psychometric properties of this new instrument
Hypotheses The use of health behavioral constructs in the development of an assessment tool will have greater predictive validity than that of existing tools
Study Design Questionnaire development and validation that involve an item development and validation stage
Number of planned patients: - 345 older adults; 345 informal caregivers
Main criteria for inclusion (inclusion/exclusion criteria) Inclusion criteria: Older adult population: 
 
• Age 60 years or older;
 
• Taking at least 5 medications daily;
 
• Having at least one chronic condition;
 
 Informal caregiver (such as spouse, family/ friend caregivers): 
 
• Self-identified as a caregiver of an older adult who has 60 years old or older, that are taking at least 5 medications daily and having one or more chronic condition;
 
• The care recipient lived in the community or in a nursing home.
 
 Exclusion criteria: Older adult population: 
 
• Suffering from psychiatric trouble;
 
• Past or present drug or alcohol dependency;
 
• Having a terminal illness;
 
• Inability to complete a written questionnaire in French due to a functional or cognitive impairment;
 
• Inability to understand and express oneself in French.
 

**Development and validation of a health behaviour theory-based questionnaire to explore the willingness of older adults and informal caregivers to deprescribe (HBQtD)**


Informal caregiver population:
 

• Caregiver age under 18 years old;

• Caregivers who are paid for the care they provide;

• Caregiver inability to give consent and complete a written questionnaire in French;

• Caregiver inability to understand and speak in French.

Procedures: Schedule of assessments – Study Flowchart

Statistical Considerations
 
Methods that will be used to validate the questionnaire: face validity, content validity, construct validity, internal validity and test-retest reliability.
 
To assess the psychometric properties of the questionnaire, an exploratory factor analysis (EFA) will be performed – construct validity. Face and content validity will be performed by qualitative methodology, and using the content validity ratio (CVR). Internal validity will be assessed using the Cronbach’s alpha and omega coefficient, and test-retest reliability will be investigated using the Cohen’s kappa and Interclass correlation coefficient (ICC). Logistic regression will be performed to investigate the association between the determinants and the intention, or deprescribing behavior.

**Development and validation of a health behaviour theory-based questionnaire to explore the willingness of older adults and informal caregivers to deprescribe (HBQtD)**

**4. SCHEDULE OF ACTIVITIES**

Activities/ Months	2023											2024								
	06	07	08	09	10	11	12	01	02	03	04	05	06	07	08	09				
Questionnaire development and protocol redaction	15d 15d 15d 15d 15d 15d 15d 15d																			
Ethics committee		15d 15d 15d 15d 15d 15d 15d 15d																		
Contact institutions and organizations for recruitment																				
Cognitive pre-test with OA and IC																				
Round with HCP																				
FG with HCP																				
Round with OA and IC																				
FG with OA and IC																				
Recruitment for questionnaire validation																				
Results analysis																				
Preparing publication																				

OA: older adults; IC: informal caregivers; HCP: healthcare professionals; FG: focus group

**Development and validation of a health behaviour theory-based questionnaire to explore the willingness of older adults and informal caregivers to deprescribe (HBQtD)**

## **5. LIST OF ABBREVIATIONS AND DEFINITIONS**

BMQ	Beliefs about medicines
BZD	Benzodiazepines
CVR	Content validity ratio
EFA	Exploratory factor analysis
HCP	Healthcare professionals
HBM	Health Belief Model
HBT	Health Behavior Theory
FG	Focus group
HL	Health literacy
HCP	Healthcare professionals
IC	Informal caregivers
ICC	Interclass correlation coefficient
NH	Nursing home
OA	Older adults
PATD	Patient Attitudes Towards Deprescribing
rPATD	Revised version Patient Attitudes Towards Deprescribing
SCT	Social cognitive theory
TPB	Theory of planned behaviour
TRA	Protection motivation theory
TTM	Trans-Theoretical Model of behaviour change
WHO	World Health Organization

## **Development and validation of a health behaviour theory-based questionnaire to explore the willingness of older adults and informal caregivers to deprescribe (HBQtD)**

### **6. ETHICS**

- *This protocol, any protocol amendments, informed consent form and other relevant documents (eg. recruitment advertisements) will be submitted to the Ethics Committee (EC) for formal approval to conduct the study. The decision of the EC concerning the conduct of the study will be made in writing to the sponsor. All correspondence with the Ethics Committee will be retained in the Investigator File.*
- *The study will be conducted in accordance with legal and regulatory requirements (Belgian law of 7 May 2004, Belgian law for Patient rights 22 August 2002, Private life GDPR 2018), as well as the Guidelines for Good Clinical Practice (International Conference on Harmonization 1996), and the last version of Declaration of Helsinki (World Medical Association).*
- *All subjects for this study will be provided a consent form describing this study and providing sufficient information for subjects to make an informed decision about their participation in this study. This consent form will be submitted with the protocol for review and approval by the EC. The formal consent of a subject, using the EC-approved consent form, will be obtained before that subject is submitted to any study procedure. This consent form must be signed by the subject or legally acceptable surrogate, and the investigator-designated research professional obtaining the consent. The written informed consent document should be prepared in the language of the potential patient population.*
- *The identity of the participant will remain kept confidential according to the General Data Protection Regulation of 27 April 2016 (in application on 25 May 2018), to the Belgian law of 30 July 2018 on the protection of natural persons with regard to the processing of personal data and the Belgian patient's right law (22 August 2002). Personal data will be coded. Subjects will not be identified by name or in any other recognizable way in any of the records, results or publications related to the experiment.*

## **7. BIBLIOGRAPHIC REFERENCES**

Prescribing medication is an essential dimension in the care of the older adults (i.e. people aged 60 or 65 and over, as per *World Population Ageing 2019: Highlights* (s. d.)), and the optimization of drug prescribing, has become an important public health issue, especially for the older adults ([name] et al., 2007). Even if, polypharmacy (i.e. five or more medications; (J. Reeve et al., 2022; Gabauer, 2020), may be appropriate in the treatment and prevention of different symptoms or disorders in older adults with multimorbidity (J. Reeve et al., 2022; Steinman, 2016; [name] et al., 2007), taking multiple medications may also be linked to a higher risk of medication-related problems. In fact, the aging process leads to physiological changes that can significantly alter both pharmacokinetics and pharmacodynamics (Pazan & Wehling, 2021). These age-related physiological changes can increase the risk of adverse drug events, and the inappropriate polypharmacy can contribute to drug-drug interaction, lower adherence to medication, significant costs to both the patient and the health care system, and also decrease the ability of people to perform activities of daily living, due to a functional decline, injurious falls, cognitive impairment, among others (O'Donnell & Ibrahim, 2022; Gabauer, 2020).

Therefore, it seems important to reflect, at different levels - micro, meso and macro, on the challenges related to the problematic polypharmacy, i.e. *“the use of multiple medicines on a long-term basis when the intended benefit of the medicines is not achieved, on the potential risks outweigh the intended benefits”* (J. Reeve et al., 2022). Indeed, this large-scale problem was recognized by the World Health Organization (WHO) that launched in March 2017 the third Global Patient Safety Challenge with the theme of medication without harm.

Deprescription, defined by Reeve et al. (2022) as *“a planned/ supervised process of dose reduction or the stopping of medicines that may be causing harm or conferring no additional benefit”*, can thus be a strategy, not only in the optimization of drug use in a context of polypharmacy, but also a strategy to revert the clinical and economic burden of polypharmacy (Reeve et al., 2022; Roux et al., 2022).

In reality, a systematic review and meta-analyses realized by Page et al. (2016), emphasized that this process of deprescribing to reduce polypharmacy is, not only feasible, but also safe. In addition, deprescribing seems to have some health benefits, and there are a trend to decrease mortality in the 65-80 years-old age group (Page et al., 2016).

Therefore, in this process of de-prescription, the patient, and even the informal caregivers, should have an active role in the health decisions that concern themselves (Chock et al., 2021; Baumgartner et al., 2020). Deprescription requires, in this way, a person-centered approach, with a shared decision-making process, and according to E. Reeve et al. (2018), some older patients are willing to be involved in this decision making process.

However, physicians report some patient reluctance or unwillingness to deprescribe, which is a very significant barrier to implementing deprescribing in clinical practice (E. Reeve et al., 2018). In fact, according to Parker et al. (2022), taking into account the patient and his impact in deprescribing, is an essential factor to understand and thus increase the effectiveness of interventions to reduce low-value care.

Therefore, as implementation deprescribing requires a complex changes to established patterns of behaviors (Scott et al., 2021), understanding the cognitive mechanisms underlying patient's and caregiver's behavior with respect to deprescribing, seems essential to improve the

## **Development and validation of a health behaviour theory-based questionnaire to explore the willingness of older adults and informal caregivers to deprescribe (HBQtD)**

collaborative work between the patient, or even the caregivers, and the health professionals, to achieve the best health outcomes for the patient (Parker et al., 2022; E. Reeve et al., 2013).

In reality, HBT provides a series of concepts deriving from social, cognitive and motivational psychology, that can be useful in understanding why people behave in certain ways in relation to their health (Gehlert & Ward, 2019). The most well-known and often-used theories are the Health belief Model (HBM; (Godin, 1991), the Theory of Planned Behavior (TPB; (Ajzen, 1991), as an extension of the Theory of Reasoned Action (TRA; (Ajzen & Madden, 1986), and the Protection Motivation theory (PMT; (Rogers, 1975). One major limitation of these models is that they actually "predict" behavioral intention, but they do not inform how to change health behaviors (Parker et al., 2022; Bandura, 2004, Godin, 1991).

Consequently, Bandura (2004) proposes a causal model, the Social Cognitive Theory (SCT), that *“offers both predictors and principles on how inform, enable, guide, and motivate people to adapt habits that promote health and reduce those that impair it”*. According to this theory, *“behavior, cognitive and other personal factors, and environmental events all operate as interacting determinants that influences each other bidirectionally”* (Bandura, 1988).

Moreover, given that behavior change involves processes that take place over time, the Trans-Theoretical Model of change (TTM; (Prochaska & DiClemente, 1983)) posits that health behavior change is a process that involves progression through a series of six stages of change: precontemplation, contemplation, preparation, action, maintenance, and termination (Prochaska & Velicer, 1997).

It is also interesting to note in Reeve et al.'s (2013) systematic review, that despite patients' ability to understand the risks and benefits associated with a certain behavior, especially about drug therapy, they showed limited ability to translate this information into decisions about whether or not the therapy is appropriate. This finding is even more striking among the elderly who often have a lack of knowledge about drug treatment and poor understanding of treatment aims, which consequently can be reflected in the inappropriate use of medicines (Parekh et al., 2018). Therefore, these elements refer to *Health Literacy* (HL), that can be defined as *“the degree to which individuals have the capacity to obtain, process and understand basic health information and services needed to make appropriate health decisions”* (Nielsen-Bohlman et al., 2004 cit by Parekh et al., 2018), and that may be an important covariant to consider in the context of deprescription.

### *Screening Tools*

In clinical practice, the existence of screening tools can be very useful, in this case to identify patients who will be more likely to respond well to therapeutic deprescription interventions (Turner et al., 2020). In reality, several tools have been developed and used, particularly in the identification of inappropriate drug use in the older patients, such as The Beers criteria (Beers, 1997) and Medication Appropriateness Index (Hanlon & Schmader, 2022). However, and despite its wide use, these tools do not provide guidance on how to stop inappropriate medication (E. Reeve, Shakib, et al., 2013).

In addition, the success of therapeutic deprescription will depend not only on medical factors, but also on patient factors. Therefore, being able to explore and objectively capture patients' beliefs and attitudes towards this therapeutic strategy seems essential (E. Reeve, Shakib, et al., 2013). Thus, other tools have been developed, including *The patients' attitudes towards deprescribing* (PATD) questionnaire, and its revised version questionnaire (rPATD; (E. Reeve

## **Development and validation of a health behaviour theory-based questionnaire to explore the willingness of older adults and informal caregivers to deprescribe (HBQtD)**

et al., 2016)), and Beliefs about Medicines Questionnaire (specific section) (BMQ-Specific) (Horne et al., 1999).

However, according to Turner et al. (2020) analyses, all 25 items found in the rPATD and BMQ-specific screening, only 8 were associated with deprescribing outcomes. In addition, these tools presents a low predictability validity for successful deprescribing (Chock et al., 2021; Turner et al., 2020), and an important gap between participants' intention and deprescribing behavior was also identified by Turner et al. (2020), with 86% of participants that are willing to deprescribe, but only 41% of participants successfully deprescribing their prescription. This significant gap and low predictive validity, can be explained by the fact that PATD and revised version was developed without a behavioral theory as a theoretical basis, whereas attitudes are a construct present in models of health behavior, such as the TPB (Ajzen & Madden, 1986). As a result, this questionnaire as well as the BMQ-specific questionnaires, do not take into account different critical domains that can be relevant to deprescribing, such as self-efficacy beliefs, outcome expectations, subjective norms, health goals, environmental barriers and enablers, among others (Linsky et al., 2015).

## **8. RATIONALE**

The studied population in this study is twofold: older adults and informal caregivers.

### *Older adults*

This study has a focus on particular population - older adult population. Advances in medicine have led to an increase in life expectancy, and a worldwide rise in the number of older people. As a result, several problems have also accompanied this increase, such as the growing number of chronic diseases and related polypharmacy, resulting in a significant burden not only for the older person, but also for healthcare systems (Pazan & Wehling, 2021).

### *Informal caregivers*

In addition, the aging process can bring about different changes and disabilities in sensory, cognitive and physical functions, which may lead some older people to choose to involve family members or close friends in managing their health (Wolff & Boyd, 2015).

### *Hypothesis*

According to Chock et al. (2021) and Turner et al. (2020) current tools, such as the BMQ and the widely used rPATD, have a number of limitations, particularly in terms of predictability validity for successful deprescribing. In addition, the rPATD items were developed without any theoretical basis in health behaviors, whereas attitudes are an important concept found, in particular, in the TPB (Ajzen & Madden, 1986). As a result, we hypothesis that the use of health behavioral constructs in the development of an assessment tool will have greater predictability validity on deprescribing behavior than that of existing tools.

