### *Expected benefits of the research*

Despite the many benefits of taking medication, multimorbidity and the chronicity of certain health problems lead to multi-medication intake, which can entail major risks for the older people. Thus, deprescribing is an important dimension in the care of the older adults, and this study intends to provide a new instrument, developed on the basis of constructs from behavioral health theories, which is expected to be more accurate than those currently in use. This tool will thus be able to provide more information about the older adults' and their caregivers' views about deprescribing and also the socio-cognitive factors that can impact their willingness to engage in deprescribing behavior. Consequently, this information could be useful in the development of interventions aimed at medication deprescribing, with a patient-centered or family-centered deprescribing approach.

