## **Development and validation of a health behaviour theory-based questionnaire to explore the willingness of older adults and informal caregivers to deprescribe (HBQtD)**

Another two questionnaires will be used in this study: one that measure health literacy (HLS19\_Q12; (Pelikan et al., 2022)) and another one that assess the locus of control (MHLC; (Wallston et al., 1978)). The previous systematic review revealed that the HL was positively associated with the willingness to deprescribe (Gillespie et al., 2019). The HLS19\_Q12 is thus the questionnaire that will be used in this study. This instrument was built on the conceptual framework and definition of comprehensive, general HL developed in the HLS\_EU (Pelikan et al., 2022). Indeed, the concept-based in the development of HLS\_EU refers to “... *people’s knowledge, motivation, and competencies to access, understand, appraise and apply information to form judgements and take decisions in terms of healthcare, disease prevention and health promotion to improve quality of life during the life course*” (Sørensen K et al., 2012 cit by (Pelikan et al., 2022)).

In addition, the locus of control was also identified in one study, in the previous systematic review, as having an impact on deprescribing behavior (Elsesser & Sartory, 1998). As a result, the Multidimensional Health locus of control scale (MHLC; (Wallston et al., 1978)) will be used. According to Lachman (1986) the multidimensional measurement is desirable for the older people, because “*it allows for the possibility of differential change trajectories across dimensions*” (Gurin & Brim, 1984 cit by Lachman, 1986), as in the aging process older people may become more sensitive to the external power or chance, but without changing one’s sense of internal control (Lachman, 1986).

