#### **1. Item Development process**

The conceptualization of the concepts used in the questionnaire was based on the results of the systematic review carried out previously. The items were built in relation to the most relevant constructs and predictors identified in the results of the systematic review, and some items from two different questionnaires (rPATD and BMQ) were also used to assess the components of some constructs, such as attitudes and perceived risk. The dimensions importance, in a first step were identified by discussion with the promotor in relation to the systematic review results. The questionnaire and items format were also discussed with the promotor, and a statistician from SMCS.

Some considerations have been taken into account in the item construction: “*Statements should be simple and short as possible, and the language used should be familiar to target respondents... Items should address only a single issue... Leading questions should be avoided, as they may bias responses. Items that all respondents would answer similarly should not be used, as they will generate little variance*” (Hinkin, 1998). In addition, items related to deprescribing behavior were regrouped and separated from those related to medication use.

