**4. Validation of the questionnaire – older adult and informal caregiver version**

The final item selection process will incorporate the results of the different qualitative analyses (interviews and FG) and quantitative analyses of the field trial data. This final version of the questionnaire will be then applied to a large sample size of older adults and informal caregiver for reliability validation.

This validity process “... refers to the degree to which evidence and theory support the interpretations of test scores for proposed uses of a test. Validity is, therefore, the most fundamental consideration in developing and evaluating tests” (AERA, APA, & NCME, 2014 cit by Clark & Watson, 2019). As a result, during this phase, a construct validity will be carried out, which is related to the “evaluation of the extent to which a measure assesses the construct it is deemed to measure” (Strauss & Smith, 2009). The internal consistency will be also calculated, as it reflects “the extent to which the questionnaire items are inter-correlated, or whether they are consistent in measurement of the same construct” (Tsang et al., 2017). Finally, a test-retest reliability will be performed, by repeating the administration of the same questionnaire with a small sample of participants (20 older adults and 20 informal caregivers) who have already completed the questionnaire. This process will ensure the consistency of questionnaire items responses across repeated administration (Tsang et al., 2017).

The two additional questionnaires (HLS19\_Q12 and MHLCS) will be administered to all participants (older adults and informal caregivers) in this final stage of the questionnaire validation process.

*Expected duration of subject participation*

Participants will be included throughout the questionnaire development and validation process, which will begin as soon as the ethics committee's opinion is received, and will continue until the sample size required for validation of the questionnaire is reached, in the final phase. The whole process is expected to take around 12 months.

*Planned timetable*

Activities/ Months	2023										2024						
	06	07	08	09	10	11	12	01	02	03	04	05	06	07			
Questionnaire development				15d	15d	15d	15d	15d	15d								
Ethics committee																	
Cognitive pre-test with OA and IC																	
Round with HCP																	
FG with HCP																	
Round with OA and IC																	
FG with OA and IC																	

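### The only stated hypothesis, better prediction of deprescribing behavior than existing tools, cannot be tested with the design described and should be restated as a concurrent association

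*Combined protocol and SAP*

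**What the plan says.** The Hypotheses row of the synopsis (Section 3) says that a tool developed from behavioral constructs "will have greater predictive validity than that of existing tools". The Hypothesis paragraph of Section 8 names BMQ and rPATD as current tools with limited predictive value, and makes the outcome explicit: the new tool "will have greater predictability validity on deprescribing behavior than that of existing tools". No other hypothesis is stated. Under Expected benefits in Section 9, the instrument is one "which is expected to be more accurate than those currently in use".

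The methods read differently. The synopsis lists the validation methods as "face validity, content validity, construct validity, internal validity and test-retest reliability", and then adds a logistic regression of the determinants on intention or deprescribing behavior. Section 9.1 (Item Development process) says that "some items from two different questionnaires (rPATD and BMQ) were also used" in building the new questionnaire. Section 9.1 also says "Another two questionnaires will be used in this study: one that measure health literacy"; the second of the two measures locus of control. Section 9.10.2 uses both as moderators.

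**The concern.** The hypothesis makes two claims at once: prediction of behavior, and superiority over named tools. Nothing in the described data collection or analysis appears to address either. If that is right, the study will end without an answer to the one hypothesis it declares. A positive regression could then be read as confirming that hypothesis when it shows only that answers given at one sitting are related. What is at stake is the hypothesis, the expected-benefits sentence and the conclusions allowed from the regression. The instrument itself is not in question.

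**Working it through.** **1. The plan's own numbers.** The participant table in Section 9.2 reproduces: 5 (cognitive pre-test) + 10 (self-administration) + 30 (pre-test) + 300 (validation) = 345 per population, and 30 = 10% × 300. Every participant is assigned to one of these steps. None of the steps is a follow-up for behavior or a comparator administration. The 300 comes from rules of thumb for exploratory factor analysis (Section 9.10.2, Sample Size). There is no power, effect size or predictive-accuracy figure for the hypothesis to reproduce.

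**2. What a test needs, set against the text.**

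- *A comparator that can be scored.* Only selected rPATD and BMQ items are used, inside the new questionnaire. A subset cannot be scored as the existing tool. The other two instruments measure health literacy and locus of control, so neither is a deprescribing comparator.
- *Behavior observed after the predictors.* Section 9.1 (Method for data collection) places past attempts, willingness and current deprescribing in the first part of the same form whose second part holds the predictor items. In the caregiver version, behavior is reported for the care recipient. Section 9.9 says that patient records are not used. Section 11 ends the study when the final questionnaire is returned. The one repeat administration in the validation step is the retest of 20 older adults and 20 caregivers. It serves reliability, and no interval is given.
- *A planned comparison.* Section 9.10.2 plans factor analysis, alpha and omega, ICC and weighted kappa, logistic regression and moderation, all on the new tool. It gives no predictive-accuracy measure and no contrast with rPATD or BMQ.

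**3. What the regression can show.** Predictors and outcome are recorded together. For past or current deprescribing, the items are answered after the behavior began, so the direction of any association stays open.

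**4. Whether willingness can stand in for behavior.** Section 7 (Screening Tools) cites a study in which 86% were willing and 41% succeeded, a gap of 86 − 41 = 45 percentage points. By the protocol's own account, willingness is not a substitute.

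**5. Whether 300 would suffice if the missing pieces were added (illustration only).** Assumptions not in the documents: comparator AUC 0.65; new-tool AUC 0.70 or 0.75; correlation r between the two AUCs of 0.3 to 0.7; behavior rate 10%, 20% or 41% (only 41% is cited in the protocol, from another study); two-sided 0.05.

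Hanley-McNeil variance: V(A) = [A(1−A) + (n₁−1)(a−A²) + (n₀−1)(b−A²)] / (n₁n₀), with a = A/(2−A) and b = 2A²/(1+A). SE² = V₁ + V₂ − 2r√(V₁V₂). Power = Φ[(A₂−A₁)/SE − 1.96].

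One case: rate 41%, so n₁ = 0.41 × 300 = 123 and n₀ = 177; A₁ = 0.65, A₂ = 0.70, r = 0.5. V₁ = 0.001065 and V₂ = 0.000980. SE = √(0.001065 + 0.000980 − 0.001022) = 0.0320. Power = Φ(1.56 − 1.96), which is about 35%.

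Over all assumptions, with n = 300:

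- AUC gain 0.05: power 11% to 52%; 579 to 4,134 respondents needed for 80%.
- AUC gain 0.10: power 34% to 99%; 139 to 995 needed for 80%.

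The range runs from clearly too small to ample, so a sample size chosen for factor analysis does not by itself support this test.

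**The case against.** The strongest reply is that the hypothesis belongs to the rationale. The primary and secondary objectives in Section 9 concern developing the questionnaire, face and content validity, and factor analysis. None mentions superiority. Section 9.10.2 words the regression modestly, as a study of association, and Section 12 promises no claim of superiority. This stands, and it limits the point. A reader might infer that the validation as a whole fails, or that the sponsor intends an unsupported claim. The documents support neither inference.

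A second reply is that the synopsis does plan to relate determinants to behavior. That is also true, so it would be wrong to say that the plan offers no evidence linking the tool to an outcome. The evidence is concurrent, though, and has no comparator.

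Third, the questionnaires are listed in Section 15 but their content is not visible, and Section 9.1 describes an initial draft. How many rPATD and BMQ items are embedded cannot be checked. The text describes only a selection, so a complete comparator scale is unlikely but not strictly excluded.

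Fourth, a reader might infer from Section 9.9, under which names are not requested, that follow-up is impossible. That goes too far. The retest already requires reaching people who have answered, and Section 9.3 has signed consents returned with the paper forms. The firmer limit is the end-of-study rule in Section 11.

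Finally, published results for rPATD and BMQ could serve as a benchmark. No such comparison is planned, and the behavior questions here cover attempts and ongoing deprescribing. The success figure cited in Section 7 is a different outcome.

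**Conclusion.** The concern holds for the hypothesis and the statements that rest on it. On the visible text, all three elements of a test are absent: a complete comparator, later behavior and a planned comparison. Followed as written, the study can report concurrent association of the new tool's items with stated willingness and with reported past or current deprescribing. It cannot report predictive validity or superiority over rPATD or BMQ. The objectives, factor analysis and reliability analyses are not affected, and no planned estimate changes. The size of the problem is therefore the gap between one declared hypothesis and the conclusion that the data allow; no numerical error is involved. The conclusion assumes that the unseen questionnaires match their description in Section 9.1.

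**What to change.** 1. In the synopsis and the Hypothesis paragraph of Section 8, restate the hypothesis as a concurrent association between the theory-based constructs and (a) stated willingness and (b) reported past or current deprescribing, which caregivers report for the care recipient. Label superiority over existing tools as an expectation for later research.
2. Under Expected benefits in Section 9, replace "which is expected to be more accurate than those currently in use" with wording such as *expected to cover determinants that existing tools do not cover*. Section 7 supports the gap, since it says that existing tools "do not take into account different critical domains that can be relevant to deprescribing". Study configuration in Section 9.1 gives the new tool's dimensions.
3. In Section 9.10.2, add that the regression supports concurrent association only, and that no conclusion of predictive validity or of superiority over rPATD or BMQ will be drawn from it.

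Cost: a few sentences and no new data. Because the hypothesis changes, Section 9.11 may require review by the promoter and then the Ethics Committee. The publishable claim becomes weaker, but the planned data could not have supported the stronger one. Keeping the superiority claim in this study would need a complete comparator scale, a later behavior measure in the same respondents, a pre-specified paired comparison with its own sample size, and data not used to select the items. That is better left to a later study.
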